Potential participants (recruited nationally) may hear about the study through a flyer given to them from clinical staff, posted on social media or websites, or through community outreach efforts. Potential participants will either a) verbally agree to clinical staff for study staff to contact participants directly, indicate interest directly into RedCAP through the QR code or by reaching out to study staff based on information they have obtained from websites or community outreach.

Potential participants will indicate their interest by completing the REDCAP screener using the QR code on the flyer or by emailing the research assistants who will provide more information about the study and schedule a screening phone call. CRCs will reach out to eligible caregivers, and engage in an informed consent discussion where they will be informed of study procedures, expectations, potential risks and benefits of participation, and information regarding who they can contact regarding further questions. They will also be informed that participation is voluntary, that they can refuse to answer any questions, and they can withdraw from the study at any time. All caregivers who verbally consent and can attend the designated time and date for the group cohort will be emailed a link with the baseline questionnaire over REDCap; a research assistant will help with questionnaire completion if needed. All baseline data collection will be completed prior to the first group session. All caregivers will also have the opportunity to attend a Zoom practice session with the Research Assistant to problem solve any technical challenges. Caregivers will complete the same questionnaires after the conclusion of the intervention. Additionally, caregivers will have access to a web-based platform. The web platform for SOCIAL will include voice over videos and recordings of skills in addition to the program manual.

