Participants will have the option to receive secure and encrypted text messages sent via Twilio, a third party, MGB-approved web service that integrates with REDCap to send reminders, survey invitations, and collect home practice participation over SMS text messaging. If participants prefer, study staff can send “unencrypted” texts that are not secure and could result in the unauthorized use or disclosure of their information or email reminders sent directly through REDCap. If participants want to receive communication by unencrypted texts despite these risks, they will be informed that MGB Healthcare will not be held responsible for any data breaches. These texts will not contain any protected health information. Text message and data rates may apply based on participants’ cell phone service plan. Participants have the right to refuse these texting reminders. This decision will not impact their ability to participate in the study. Participants can opt out of these text messages at any time.

Outcome Measures

Primary Outcome Measures

1. Feasibility of Recruitment

We will examine feasibility of recruitment through tracking of the number who respond through flyer (QR Code), email, website or direct clinical contact.

[Time Frame: Baseline]

2. Feasibility of Assessments

We will calculate the proportion of caregivers completing the study questionnaires.

[Time Frame: Baseline, Post-intervention]

3. Feasibility of Quantitative Measures

We will assess the proportion of quantitative measures missing within the questionnaires.

[Time Frame: Baseline, Post-intervention]

Other Pre-specified Outcome Measures

4. Symptoms of Depression

We will use the Center for Epidemiological Studies-Depression Scale (CES-D). This is a 20-item scale widely used with ADRD caregivers.

[Time Frame: Baseline, Post-intervention]

5. Mindfulness

We will use the Five Facets Mindfulness Questionnaire FFMQ (15 items) to assess caregivers' mindfulness based on 5 subscales (observing, describing, awareness, non-judging, non-reactivity).

[Time Frame: Baseline, Post-intervention]

6. Perceived Stress

We will use the PSS-10 (10 items) to assess perceived stress.

[Time Frame: Baseline, Post-intervention]

7. Symptoms of Anxiety

We will use State Trait Anxiety Inventory (STAI) state subscales (20 items) to assess anxiety symptoms in response to stressful situations. STA has been successfully used with ADRD caregivers.

[Time Frame: Baseline, Post-intervention]

8. Self-Compassion

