20. Perceptions of Email and Text Reminders

We will assess caregivers' perception of emails and text messages reminders by asking, "Do you think that the amount of emails/texts you received was: too little, just enough, too much?"

[Time Frame: Post-intervention]

21. Credibility and Expectancy

We will use the Credibility and Expectancy Questionnaire (CEQ), (6 items) to assess caregivers' perceptions that the treatment will work after participating in the intervention.

[Time Frame: Pre-intervention]

The self-report measures and assessment domains align with the purpose of the study and with recommendations for feasibility trials. Feasibility of recruitment and retention will be assessed using proportions (see Table 1). Satisfaction and credibility will be assessed with proportions of scores over the midpoint of the Client Satisfaction and Credibility and Expectancy questionnaires.

4. Subject Selection

Study Population Characteristics

Conditions or Focus of Study

- Informal caregivers of people with ADRD who endorse caregiver stress and challenges managing patient behaviors

Eligibility Criteria

Caregivers will be 18 years or older, fluent in English, who meet the criteria for an informal caregiver (e.g., family or friend of a care recipient who provides unpaid care) and lives with and cares for an individual with ADRD. The informal caregivers must have lived with the patient for more than 6 months and must currently provide more than 4 hours of supervision or direct assistance to the care recipient per day (average). Caregivers will need to endorse stress (PSS-4 \geq 6) and self-report that they had managed 1 or more behavioral symptoms in the past month. Exclusion criteria include planned change in psychotropic treatment for the duration of the study, use of mindfulness apps or any meditation (more than 60 min/week in past 6 months), major illness known to drastically worsen or require surgery for the duration of the study, active treatment for cancer, involvement in another clinical trial for caregivers, a score \geq 4 on the PMSQ and no stated concerns or distress related to care recipient's disruptive behaviors.

Inclusion Criteria

- 18 years or older
- English fluency and literacy
- Meeting criteria for being a caregiver (e.g., family or friend of a care recipient who provides unpaid care)
- Must live with and care for an individual with ADRD.
- Must have been in a caregiver role for more than 6 months

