- Must provide an average 4 hours of supervision or direct assistance per day for the care recipient
- Perceived Stress Scale-4 (4-item) version \geq 6
- Had managed 1 or more behavioral symptoms in past month

Exclusion Criteria

- Recent change in psychotropic treatment for depression or anxiety.
- Use of mindfulness apps or any meditation (more than 60 min/week in past 6 months).
- Involvement in another clinical trial for caregivers, a score \geq 4 on the Portable Mental Status Questionnaire (PMSQ).
- No stated concerns or distress related to care recipient's disruptive behaviors.
- Involvement in another clinical trial for caregivers

Recruitment and Retention Plan

We will conduct a live video (Zoom) open pilot group with exit interviews (N=up to 2 groups, up to 20 caregivers). We will use this information to revise SOCIAL and our conceptual model, as needed to maximize feasibility and target engagement.

5. Subject Enrollment

Potential participants recruited nationally will indicate their interest by completing the REDCap screener using the QR code on the flyer or by emailing the research assistants who will provide more information about the study and schedule a screening phone call. CRCs will reach out to eligible caregivers and engage in a discussion where they will be read the study fact sheet which including an explanation of study procedures, potential risks and benefits of participation, and information regarding who they can contact regarding further questions via a phone call, and if they would like to consent to participate. They will also be informed that participation is voluntary, that they can refuse to answer any questions, and they can withdraw from the study at any time. All caregivers who consent and can attend the designated time and

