date for the next group cohort will be emailed a link with the baseline questionnaire over Redcap and offered assistance with questionnaire completion from the research assistant. Caregivers who provide consent but are unavailable to participate in the next available group will be placed on a waitlist for the next group cohort. All baselines will be completed within 1 week of the first group session. Due to the remuneration amount, participants will be prompted to complete an MGB secured REDCap survey along with the initial pre-intervention (baseline) survey that will ask for their SSN per MGH's compensation policy. If participants do not want to provide their SSN, an option will be provided to them of receiving \$50 through two gift cards (see Renumeration below). Additionally, prior to the first intervention session, caregivers will have the opportunity to attend a zoom practice session with the Research Assistant to problem-solve any technical challenges.

6. Study Procedures

Study enrollment

We will recruit up to 20 caregivers for up to 2 groups in this study. Participants will be asked to complete a baseline assessment that asks questions on physical and mental wellbeing as well as questions about their experiences as a caregiver for someone living with dementia. Upon completion, caregivers will be invited to participate in a weekly 60-minute virtual group training session for 6 weeks that is led by a trained Clinical Social Worker. The content of each session varies week-to-week: Week 1: *Understanding Caregiver Stress and Distress*; Week 2: *Mindful Caregiving*; Week 3: *Caring Without Losing Ourselves*; Week 4: *Behavior Management Skills*; Week 5: *Mindful and Self-Compassionate Caregiving*; Week 6: *Mindful and Self-Compassionate Life*. At the end of the 6 weeks, we will conduct individual live video exit interviews to gather detailed feedback on SOCIAL intervention components, applicability of study measures, general protocol issues including barriers and facilitators to participation and skill practice, perception of the web platform, and perception of the live video intervention delivery. Exit interviews will last 30 minutes and will be recorded via zoom, transcribed using Landmark Associates, and analyzed in NVivo to refine study procedures and finalize SOCIAL before the pilot RCT.

7. Risks and Discomforts

Potential risks

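### Does wording the recruitment outcome as a count of responders leave the pilot without a usable recruitment rate?

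*Combined protocol and SAP*

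**What the plan says.** Under Outcome Measures in section 3, primary outcome 1 (Feasibility of Recruitment) reads "We will examine feasibility of recruitment through tracking of the number who respond through flyer (QR Code), email, website or direct clinical contact". The next two primary outcomes are worded as proportions: "We will calculate the proportion of caregivers completing the study questionnaires" and "We will assess the proportion of quantitative measures missing within the questionnaires". The paragraph that closes Outcome Measures, just before section 4, says of recruitment: "Feasibility of recruitment and retention will be assessed using proportions (see Table 1").

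The route into the study has several steps. In section 3, "Potential participants will indicate their interest by completing the REDCAP screener using the QR code on the flyer or by emailing the research assistants". In section 5, "CRCs will reach out to eligible caregivers and engage in a discussion where they will be read the study fact sheet". Caregivers who consent but cannot attend the next group "will be placed on a waitlist for the next group cohort". Enrolment is capped in section 6: "We will recruit up to 20 caregivers for up to 2 groups in this study". Section 3 adds that recruitment efforts are logged in a secure database, which is meant to firm up the recruitment plan for the later pilot trial.

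**The concern.** Read alone, primary outcome 1 is a numerator without a denominator. Response is the first step of the pathway; screening, eligibility, the consent discussion and group placement come after it. A responder count therefore does not show how many eligible caregivers agree to join. The enrolled count does not show it either, because it stops at 20 and some consenting caregivers may be waitlisted.

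Feasibility is part of Hypothesis 1, and the recruitment experience is meant to inform the next pilot. If only responders and enrolments were reported, the next team could not tell whether caregivers were lost at eligibility (which points to sources or criteria) or at consent (which points to the offer itself). A reader might also worry that an unspecified ratio could be chosen once the counts are known. The contrast with outcomes 2 and 3, both worded as proportions, makes the omission look like an error.

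**Working it through.** **1. Is there a figure to reproduce?** No. The documents give no recruitment target, expected response, eligibility rate or consent rate, and section 9 sets aside conventional power analysis. All recruitment counts below are assumptions, apart from the stated cap of 20.

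**2. Can a responder count hide different consent rates?** Assume 70 responders and 24 consents, of whom at most 20 can be placed (24 − 20 = 4 not placed). For x out of n the proportion is x/n. The exact (Clopper-Pearson) 95% limits are the 0.025 quantile of Beta(x, n − x + 1) and the 0.975 quantile of Beta(x + 1, n − x).

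| Quantity | Case A: 30 eligible and offered | Case B: 60 eligible and offered |
|---|---|---|
| Consents per responder | 24/70 = 34% (23–47%) | 24/70 = 34% (23–47%) |
| Responders per consent | 70/24 = 2.9 | 70/24 = 2.9 |
| Eligible among responders | 30/70 = 43% (31–55%) | 60/70 = 86% (75–93%) |
| Consent among those offered | 24/30 = 80% (61–92%) | 24/60 = 40% (28–53%) |
| Consent discussions per consent | 30/24 = 1.25 | 60/24 = 2.5 |

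So the arithmetic behind the concern is right: a count does not fix a ratio. Consents per responder, which tells the next trial how much outreach it needs, is the same in both cases.

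**3. Do the two statements about recruitment conflict?** Primary outcome 1 says what will be tracked. The closing paragraph says how recruitment will be assessed, namely by proportions, with the detail in Table 1. The tracked number can serve as the denominator of such a proportion, so both statements can be true together. Table 1 is not in the text available here, so its definition, or any benchmark in it, can be neither confirmed nor denied.

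**4. Would the step counts be lost?** Each step has a natural source in the procedures:
- responders: the tracking in outcome 1;
- eligible: the REDCap screener and the screening call;
- consented: the consent discussion;
- not placed: the waitlist;
- enrolled: the group roster, up to 20.

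Section 3 says recruitment efforts go into a database. The text does not promise to report every step rate, but the wording of one outcome does not remove data that the procedures generate. Cases A and B look alike only to someone who sees responders and enrolments and nothing else.

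**5. Would a decision change?** The available text sets no recruitment threshold. The go/no-go benchmark in section 9 concerns whether the minimal clinically important difference lies within the 95% confidence interval for the quantitative measures; it does not concern recruitment. Any consent rate would also be imprecise at this size. At 50% consent, 15/30 gives 31–69% (half-width 18.7 points) and 30/60 gives 37–63% (13.2 points).

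**The case for a change.** The best argument for a change is that capturing data is not the same as pre-specifying an outcome. A primary outcome should say what is divided by what, the two neighbouring outcomes do so, and this one does not refer to Table 1. The edit would be cheap, and it would close off a choice of ratio after the counts are known.

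Part of this stands: naming the numerator and denominator next to outcome 1 would read better. Three things keep it from being more than a drafting preference.

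- The plan does state that recruitment is assessed by proportions and says where the detail lies. Treating the definition as absent would hold an unseen table against it.
- Consent among eligible caregivers is not named in the documents as the intended ratio. Consents per responder fits the closing paragraph equally well. Consent to an open pilot in which everyone receives the intervention may also not carry over to a randomised pilot, which weakens the case for making that rate the headline.
- The alternative has loose ends of its own. A denominator of caregivers offered participation leaves out eligible caregivers whom staff never reach. Eligibility is also not worded identically throughout section 4: the narrative excludes a planned change in psychotropic treatment, the list a recent one.

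The worry about choosing a ratio afterwards has little force where no visible threshold separates success from failure and the full flow can be reported.

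**Conclusion.** No change to the plan is needed. Outcome 1 is worded as a count, and a count cannot show the consent rate; with the same 70 responders and 24 consents, that rate could be 40% or 80%. But the plan already says that recruitment is assessed by proportions, the count can feed such a proportion, and the recruitment database and screening steps should supply the other counts. An analyst reporting this pilot would give the flow from response to enrolment with the ratios that follow from it, and would count waitlisted caregivers as having consented.

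This conclusion assumes that Table 1 exists in the full protocol, or that the analysts define the proportion in keeping with the closing paragraph, and that the database records eligibility and consent as well as first contact. If Table 1 gives the definition, the remaining mismatch is editorial. If it does not, the gap is still one of detail. No stated result or decision has been shown to change, and the percentages above are illustrations, not estimates for this study.

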We will use the NIH stage model and principles from the Science of Behavior Change (SOBC) to develop, optimize and establish proof of concepts for the Supporting Our Caregivers In ADRD Learning (SOCIAL) for stressed caregivers of persons with ADRD with challenging behaviors, with a strong focus on mechanisms of action. SOCIAL structure and components will be designed to facilitate uptake (video delivery, shorter program, simple, lay language), skills practice (web platform downloaded as an app with all program skills; focus on incorporating skill practice within the caregiver activities) and sustainability of effects (continued access to the web platform with skills after the group sessions end). We will enroll stressed caregivers (PSS-4≥ 6) who self-report managing 1 or more patient behaviors in the past month from the Dementia Care Collaborative Program at MGH ([name] director), Massachusetts Alzheimer's Disease Research Center community partners, and from national dementia care programs (>38% racial and ethnic minorities as benchmark).

Significance

Informal caregivers are the backbone of our health care landscape. A caregiver—sometimes called an informal caregiver—is an unpaid individual who provides assistance (physical and/or emotional) to one or more individuals with chronic illness, frailty, disability, or a mental health disorder.¹ Over 11 million caregivers provide unpaid care to an older adult with Alzheimer's Disease or Related Dementia (ADRD).² The lifetime cost of caring for one person with ADRD exceeds \$350,000 and family care accounts for 70% of this toll.³ Despite their critical role in supporting persons with ADRD, caregivers are often described as “hidden patients” because they are at risk for negative health outcomes but are underrecognized and undertreated.⁴

Caregiver stress, emotional distress (symptoms of depression and anxiety) and reduced well-being are common among caregivers of persons living with ADRD, are exacerbated by care recipient behavioral symptoms and negatively impact morbidity and mortality for both themselves and the person they care for. Although some caregivers adjust well to their role of caring for an individual with ADRD, approximately 40% report stress that negatively impacts their health and well-being.^{5,6} Caregiver stress (also known as caregiver stress syndrome) is defined as the strain or load borne by a person who cares for a chronically ill, disabled, or older family member.⁷

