Building on the limitations of prior research, we proposed to develop the **Supporting Our Caregivers In ADRD Learning (SOCIAL)** to help caregivers of persons with ADRD manage the stress associated with the general caregiver experience including stress stemming from managing challenging patient behaviors. In AIM 1 of the SOCIAL study (Protocol#: 2022P002037) we obtained feedback on the program's proposed content and format from caregivers of individuals living with ADRD. What we learned from those responses was used to inform this open pilot (aim 2) of the study which aims to teach: (1) mindfulness skills; (2) compassion and self-compassion skills; and (3) behavioral management skills. The SOCIAL open-pilot also provides psychoeducation and group-based training and skill practice to facilitate skill uptake and integration within the caregiver experience and tasks.

2. Specific Aims and Objectives

We will conduct a live video open pilot of the SOCIAL intervention with exit interviews (N=up to 2 groups, up to 20 caregivers). We will use this information to revise SOCIAL and our conceptual model, as needed to maximize feasibility and target engagement. Hyp. 1: SOCIAL will show evidence of feasibility, acceptability, credibility, and fidelity. Hyp. 2. SOCIAL will show evidence of improvement in intervention targets and outcomes and these improvements will be correlated.

3. General Description of Study Design

We will conduct an open pilot of our active intervention, SOCIAL, delivered via live video (Zoom) to ADRD caregivers who meet eligibility criteria. We will recruit and enroll up to 20 stressed informal caregivers of ADRD individuals who also report challenges managing patient behaviors. Participants will be adults (18 years or older) who care for an individual with ADRD and who endorse caregiver stress on the Perceived Stress Scale-4 (score of 6 or higher) and have managed 1 or more behavioral symptoms in the past month. We will recruit caregivers from an array of sources, including, but not limited to, local caregiver support programs, dementia research centers, and community partners. All recruitment efforts will be captured in a secure database and will allow us to solidify our recruitment plan for the subsequent pilot clinical trial.

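### Do the overlapping response routes in primary outcome 1 (Feasibility of Recruitment) make the recruitment count unreliable?

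*Combined protocol and SAP*

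**What the plan says.** Under Primary Outcome Measures, item 1 (Feasibility of Recruitment, time frame baseline), the plan states: "We will examine feasibility of recruitment through tracking of the number who respond through flyer (QR Code), email, website or direct clinical contact".

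Section 3 (General Description of Study Design) describes how people hear of the study and how they reply. They may hear through "a flyer given to them from clinical staff, posted on social media or websites, or through community outreach efforts". They may then agree verbally with clinical staff to be contacted, use the QR code to enter REDCap, or respond "by reaching out to study staff based on information they have obtained from websites or community outreach". The next paragraph says that interest is shown by "completing the REDCAP screener using the QR code on the flyer or by emailing the research assistants".

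Section 3 also names recruitment sources, among them "local caregiver support programs, dementia research centers, and community partners". It says that every recruitment effort is logged in a secure database, and that this "will allow us to solidify our recruitment plan for the subsequent pilot clinical trial".

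The paragraph that closes the outcome list adds: "Feasibility of recruitment and retention will be assessed using proportions (see Table 1"). That table is not in the supplied text, so nothing here depends on what it contains.

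**The concern.** The four labels do not lie on one axis. QR code and email describe how a person replied. Website describes where the person heard of the study. Direct clinical contact can be taken either way. Two people tabulating one log could therefore report different splits, and adding up the categories could count some people twice. Social media and community outreach have no label of their own, and the named programs and centers cannot be identified from the four labels.

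This is the first of three primary outcomes, and recruitment experience is meant to inform the later pilot trial. If the split were unstable enough to change which route appears most productive, the next trial could put its effort in the wrong place. The introductory text before Significance also sets a diversity benchmark beside one source ("from national dementia care programs (>38% racial and ethnic minorities as benchmark"), which might suggest that the source must be recoverable from this outcome.

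**Working it through.** The plan states no responder number, recruitment target or power calculation, so there is no figure of its own to reproduce. The check is on classification.

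**Step 1: match reply routes to categories.**

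| Reply route in Section 3 | Category in outcome 1 |
|---|---|
| Verbal agreement with clinical staff to be contacted | Direct clinical contact |
| QR code into REDCap | Flyer (QR code) |
| Email to the research assistants | Email |
| Contact with staff prompted by a website | Website (also email, if that is how they wrote) |

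Every reply route has a category. The list does not contradict Section 3.

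**Step 2: count the ambiguous paths.** Take four sources (clinic flyer, social-media flyer, website, outreach), each with a QR or email reply, plus verbal agreement for the clinic only: 4 × 2 + 1 = 9 paths.

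- Narrow reading (QR code, email and clinical contact are reply modes; website is a source): 0 of 9 paths lack a category. Two of 9 fit two categories: website then QR, and website then email.
- Broad reading (flyer and clinical contact may also be sources): 0 of 9 lack a category, and 6 of 9 fit two or more.

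Social-media and outreach responders fall under flyer or email on both readings. They are counted; only their source goes unreported.

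**Step 3: size of the effect, in an assumed example.** The plan gives no numbers. Suppose 60 unique responders: clinic verbal 10, clinic flyer scanned 15, website flyer scanned 5, website then email 10, social-media flyer scanned 10, outreach then email 10.

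On the narrow reading only the 5 + 10 = 15 website-sourced people are ambiguous.

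| Category | Lowest | Highest |
|---|---|---|
| Flyer (QR code) | 15 + 10 = 25 | 25 + 5 = 30 |
| Email | 10 | 10 + 10 = 20 |
| Website | 0 | 5 + 10 = 15 |
| Direct clinical contact | 10 | 10 |

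The lowest flyer count (25) exceeds the highest email count (20) and the highest website count (15), so the leading route does not change. Entering each person in every category that fits gives 60 + 15 = 75 entries, but still 60 people.

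**Step 4: what a larger swing would need.** If the 15 people who scanned a clinic flyer are also allowed to count as direct clinical contact, that category runs from 10 (10/60 = 17%) to 10 + 15 = 25 (25/60 = 42%), and entries rise to 75 + 15 = 90. Sorting purely by where people heard gives clinic 25, website 15 and 10 + 10 = 20 (20/60 = 33%) with no label. That last tabulation discards two of the four stated categories, flyer (QR code) and email, so it measures a different quantity from the one in the plan.

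**Step 5: general form.** With n unique responders, w of them from a website, the narrow reading lets the website count be anything from 0 to w. The unique total stays n, and multiple entry gives n + w. For an assumed n = 20 and w = 4, 8 or 12, that is 24, 28 or 32 entries for 20 people.

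**The case for a change.** The strongest opposing case is that the overlap survives even the charitable reading. Website has no reply mode of its own, so anyone who comes from a website and uses the QR code or email fits two labels, and no visible text says which to use. A flyer handed over in clinic and then scanned could also be logged two ways. A primary outcome should come out the same whoever tabulates it, and source is hard to recover if it is not asked at first contact. Two recorded items, source and reply mode, would cost little.

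The website overlap stands, and so does the absence of a written rule. Yield from social media or outreach cannot be read from this outcome as worded.

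The clinic overlap is weaker. The parenthesis ties the flyer category to the QR code, and Section 3 gives verbal agreement with clinical staff as a separate route, so a scanner belongs most naturally under flyer. The need for source data is also weaker than it looks: Section 3 ties the later recruitment plan to the database of recruitment efforts, not to this outcome. That database may record source, although the text does not say so. The diversity benchmark is a matter of who is recruited, and checking it needs race and ethnicity data, not a route label.

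**Conclusion.** No change to the plan is needed. The gap is an unwritten sorting rule for a descriptive count. It affects only the split by route. It does not affect the number of unique responders, and nobody goes uncounted. In the assumed example, up to 15 of 60 people could move between categories, and the leading route stays the same.

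Little depends on the split. The supplied text sets no threshold, test or go/no-go rule on any route. Section 9 describes the work as exploratory, meant to refine the intervention and protocol, and enrolment is capped at 20. An analyst would count each person once, sort by how they replied, and note website origin where it is known.

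This conclusion assumes that the labels are read mainly as reply modes, as their match with Section 3 suggests. The larger swings need the clinic label read as a source, or a tabulation that drops two of the stated categories. The example counts are assumed, since the plan gives none. Table 1 could not be checked; it may define the categories or the proportions more fully.
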